**RANDOMIZED LIFESTYLE INTERVENTION IN OVERWEIGHT AND OBESE PREGNANT
HISPANIC WOMEN**

PROTOCOL

NCT01868230

Document Date: 6-9-2014

Approach & Methods

D1. Study Overview

The overall goal of this randomized controlled trial is to test the efficacy of a culturally and linguistically modified, individually tailored lifestyle intervention to reduce excess gestational weight gain (GWG), increase postpartum weight loss, and improve maternal metabolic status among overweight/obese Hispanic women. Specific aims are to evaluate the impact of the intervention on 1) GWG and postpartum weight loss, 2) pregnancy and postpartum biomarkers of insulin resistance (i.e., glucose, insulin, HbA1c, HOMA, leptin, adiponectin), 3) postpartum biomarkers of cardiovascular risk (i.e., blood lipids, blood pressure), 4) offspring outcomes (i.e., anthropometric measures and biomarkers of insulin resistance), and 5) to evaluate the cost-effectiveness of the intervention per average incremental improvement in the outcome variables. Overweight/obese Hispanic women will be recruited in early pregnancy (around 10 wks gestation) and randomly assigned to a Lifestyle Intervention (n=150) or a Comparison Health and Wellness (control) Intervention (n=150). The intervention will utilize exercise (R01NR011295) and dietary intervention materials (R18DK067549) culturally adapted for Hispanics and shown to be efficacious in our previous controlled trials in this ethnic group. Multimodal contacts (i.e., in-person, telephone counseling, and mailed print-based materials) will be used to deliver the intervention during pregnancy (~12 wks gestation to delivery) continuing into postpartum (~6 wks to 6 mos postpartum); follow-up will continue for one year postpartum. Targets of the intervention are to achieve Institute of Medicine Guidelines for GWG and postpartum weight loss; ACOG guidelines for physical activity through increasing walking and developing a more active lifestyle; and reduction in total calories by following a balanced healthy diet in compliance with American Diabetes Association guidelines. The intervention draws from Social Cognitive Theory and the Transtheoretical Model and includes strategies for partner and/or family support to address the specific social, cultural, and economic challenges faced by underserved Hispanic women. Measures of compliance will include actigraphs and Hispanic food frequency questionnaires. The proposed project builds upon the expertise of the investigative team in conducting randomized controlled trials of exercise interventions among Hispanic pregnant women (R01 DK074876) and dietary interventions among low-income Hispanics with type 2 diabetes (R18 DK0658850) and can readily be translated into clinical practice in underserved and minority populations.

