To ensure retention and to control for contact time, the Comparison Health & Wellness arm receives mailed materials and telephone booster calls on the same schedule as the Lifestyle Intervention arm (Figure 1). In this way, we control for contact time, while keeping the content of the two interventions distinct. These booklets represent high-quality, standard, low-cost, self-help material currently available to the public which focus on non-exercise and non-dietary topics in both English and Spanish. These include the ACOG series of informational booklets on general issues related to health and wellness during pregnancy (e.g., Alcohol and Drug Use during Pregnancy, Easing Back Pain) and the American Academy of Pediatrics booklets on parent resources (e.g., Parenting your Infant). Hispanic control-arm participants in our prior studies (R01DK074876, R01NR011295, R21NR009864) reported that these materials were of interest¹⁴⁹ and differential dropout did not occur between study arms.

D.12. Outcome Variables

D.12.1. Biomarkers of Insulin Resistance and Other CVD Risk Factors

Fasting samples will be collected at a Baystate Reference Laboratory at baseline (~10 weeks gestation), 24-28 wks, and 32-34 wks gestation during routine prenatal care visits, and at 6 wks, 6 mos, and 1 yr, and among children at ~1 yr postpartum (coordinated with timing of the routine lead/CBC screen) (termed “blood draw”). Samples will be stored at -80 degrees Celsius in a freezer at Baystate with temperature monitoring, alarm and a back-up power system. Samples will be shipped periodically to the assaying lab. Residual blood samples will be stored at [name] lab to resolve potential data validation questions related to this study, and will be destroyed 7 years after study completion, unless the participant agrees to storage for future studies (included as “opt-in” in the informed consent form). Quality control for specimen handling will be performed monthly by the head lab technician. Samples will be assayed by [name] (Department of Laboratory Medicine, Harvard University) at Children’s Hospital, Boston, MA.

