Specific Aim #1, 2, 3: Impact of a Lifestyle Intervention on GWG and postpartum weight loss; biomarkers of insulin resistance; postpartum biomarkers of CVD risk. The primary analysis will evaluate differences in the change from baseline in weight gain measures, glycemia and other biomarkers of insulin resistance and cardiovascular risk factors between the groups (an intent to treat analysis). Initial analyses will describe the correlation of factors and investigate simple transformations for normality. The primary analysis will be based on a mixed model with random subject effects, including a common mean at baseline for the intervention groups, a period effect, and an intervention by period interaction.¹⁷⁰ The intervention by period interaction is a measure of the intervention effect, and corresponds to the estimate of an intervention effect in an analysis of covariance. The mixed model analysis will enable inclusion of time varying covariates such as depression, breastfeeding behaviors, and sleep, which may vary between baseline and follow-up for subjects. Equivalence of the intervention groups will be assessed by comparing the distribution of the potential confounders between each group. We will investigate established risk factors for weight gain (e.g., parity) and glycemia as well as degree and treatment for abnormality on glucose tolerance testing during pregnancy (e.g., diet, oral hypoglycemic and/or insulin) as potential confounders or effect modifiers. Generally, we will consider a change in the parameter estimate for the exposure (at least 15%), relative to that observed when not controlling for the variable as reflective of confounding. Effect modification will be evaluated by inspection of stratum specific odds ratios as well as by evaluating the statistical significance of interaction terms via likelihood ratio tests. We will also model the relationship between measured levels of exercise, sedentary behavior, and diet with each outcome, while adjusting for possible confounders using mixed effect linear regression models. We will test hypotheses with 2-sided tests. Finally, we will compare adoption and maintenance of behavior change (i.e., exercise, diet) in the intervention group relative to the control group by adding a fixed treatment group effect.

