Specific Aim #4: Evaluate the impact of a Lifestyle Intervention on the outcomes of offspring. We will evaluate the impact of intervention arm on the offspring outcomes using the methods described for Aim #1-3. We will also examine GWG and prenatal glycemic factors as predictors of glycemia and weight gain in early infancy and childhood. Important covariates are listed in the covariate section. In models focused on offspring weight gain as the outcome, we will additionally adjust for fetal growth (i.e., BW/GA z score).

Specific Aim #5: Evaluate the cost-effectiveness of the Lifestyle Intervention. We will use procedures developed in our prior studies examining the cost-effectiveness of our interventions.¹⁷¹⁻¹⁷³ We will calculate the ratio of average dollars spent per average incremental improvement in outcome (i.e., GWG, postpartum weight retention, and biomarkers of insulin resistance and CVD risk). Incremental improvement will be defined as the mean change score from baseline for each group, adjusted for baseline values of the outcome measure and other participant characteristics.

Accounting for Missing Data: Although every effort is made to avoid missing data, we plan to use propensity score techniques¹⁷⁴⁻¹⁷⁶ to evaluate the potential sensitivity of results to missing at random assumptions. Multiple comparisons will be addressed by carefully considering the biologic rationale of observed associations.

D.17. Power

To achieve power to detect clinically significant differences requires 300 participants (150 in each intervention arm) at the time of delivery. Based on observed rates in our 2 trials (R01DK074876 and

ASPH/CDC S3948), we conservatively expect 10% of women to leave the New England area, deliver elsewhere, or withdraw during pregnancy, and therefore will recruit 333 women over the 24 mos recruitment period. For offspring outcomes, we calculate that 4% will be excluded for very early preterm birth (<34 wks), miscarriage, or stillbirth resulting in 288 children at delivery. Over the following 1 yr, we conservatively project that an additional 8% of women will be lost to follow-up due to withdrawal or movement out of the New England area. Women who become pregnant again will be censored. Therefore, we expect 264 women and children at 1 yr postpartum.

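### Aim 5 defines the cost-effectiveness ratio from each arm's own change and average spend, so as written it is not incremental

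*Combined protocol and SAP*

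**What the plan says.** Section D1 sets the fifth aim as "to evaluate the cost-effectiveness of the intervention per average incremental improvement in the outcome variables". The analysis is specified only in D.16, under Specific Aim #5. The quantity to be reported is the "ratio of average dollars spent per average incremental improvement in outcome", and the outcomes named are GWG, postpartum weight retention, and the insulin-resistance and cardiovascular biomarkers. The next sentence defines the denominator: "Incremental improvement will be defined as the mean change score from baseline for each group", with adjustment for the outcome's baseline value and for other participant characteristics. For the method, the section refers to earlier work: "We will use procedures developed in our prior studies examining the cost-effectiveness of our interventions". Those procedures are cited but not reproduced.

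Two other places bear on this. For Aims 1-3, D.16 says "The intervention by period interaction is a measure of the intervention effect", which is a between-arm quantity. D.11 says the comparison arm "receives mailed materials and telephone booster calls on the same schedule as the Lifestyle Intervention arm", so that arm also consumes resources.

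**The concern.** A cost-effectiveness ratio should say what the extra spending on one option buys over the alternative. Both its parts are therefore differences between arms. Here the denominator is defined within each group and the numerator is average spend, with no subtraction in either. Adjusting for baseline values and participant characteristics balances the arms, but it leaves in place whatever change both arms share. In pregnancy and the year after delivery, that shared change may be large.

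At stake is whether Aim 5, one of five specific aims, can answer its question. Two analysts, one following the definition to the letter and one reading a contrast into the word incremental, could report very different dollar figures from the same data. For GWG the literal reading gives no usable figure.

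**Working it through.** **Inputs from the documents.** D.17, Table 3: postpartum weight loss, N = 264, SD 6.00, detectable between-arm difference 2.1 (no unit is printed; taken as kg); GWG, N = 300, SD 7.00 kg, detectable difference 2.3 kg; two-sided alpha 5%, power 80%. D.12.3: GWG is delivery weight minus pre-pregnancy weight.

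**Assumptions, because the documents give no figure.** Cost per woman: Lifestyle C_L = $300; comparison C_H = $0 or $150. Comparison-arm mean improvement m: from -3 kg (net retention) to +6 kg (net loss).

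**1. Reproduce the plan's figures.** Detectable difference = (1.960 + 0.842) × SD × √(4/N).
- Postpartum: 2.802 × 6.00 × √(4/264) = 2.07, against 2.1 stated.
- GWG: 2.802 × 7.00 × √(4/300) = 2.26, against 2.3 stated.

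Both agree to rounding, and both are differences between arms. I use them as the true effect d.

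**2. Set out the two ratios.**
- As written, Lifestyle arm: C_L / (m + d).
- Incremental: (C_L − C_H) / d.
- Incremental divided by written: [(C_L − C_H)/C_L] × (m + d)/d.

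The incremental ratio does not depend on m; the written one does.

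**3. Postpartum weight, d = 2.1.** The incremental ratio is 300/2.1 = $142.9 per kg if C_H = $0, and 150/2.1 = $71.4 if C_H = $150, at every m.

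| m (kg) | m + 2.1 | Written ratio, $ per kg | Incremental ÷ written, C_H = $0 | Incremental ÷ written, C_H = $150 |
|---|---|---|---|---|
| -3 | -0.9 | negative | no meaning | no meaning |
| -1 | 1.1 | 272.7 | 0.52 | 0.26 |
| 0 | 2.1 | 142.9 | 1.00 | 0.50 |
| 2 | 4.1 | 73.2 | 1.95 | 0.98 |
| 4 | 6.1 | 49.2 | 2.90 | 1.45 |
| 6 | 8.1 | 37.0 | 3.86 | 1.93 |

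Values above 1 mean that the written ratio makes the intervention look cheaper than it is; values below 1, dearer. With C_H at half of C_L, the crossing point is m = d = 2.1 kg.

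Reporting the ratio by arm does not repair this. At m = 4 and C_H = $150, the comparison arm's own ratio is 150/4 = $37.5 against $49.2 for Lifestyle. The comparison arm looks the better buy, and nothing in either figure shows that Lifestyle achieved 2.1 kg more.

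**4. GWG, d = 2.3 kg.** If the comparison arm gains 8 to 14 kg (assumed), the Lifestyle arm gains 5.7 to 11.7 kg. The within-arm change has the wrong sign for an improvement. If the sign is ignored, $300 divided by the gain falls from $52.6 at 5.7 kg to $25.6 at 11.7 kg, so more gain looks cheaper. The between-arm effect is 2.3 kg avoided throughout: 300/2.3 = $130.4 per kg if C_H = $0.

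**The case against.** The strongest reply is that the sentence calls for an adjusted mean change for each group, so it produces the inputs for both arms, and the word incremental together with the cited procedures may imply that they are then differenced. That may be what the authors intend. The cited work cannot be seen here, so it cannot be said that the analysis actually performed would be non-incremental. What does not stand is that this settles the matter. The plan defines the term explicitly, the definition is per group, and no later step subtracts either change or cost. If the cited procedures do difference the arms, the written definition still has to be corrected to match.

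A reader might also infer that the written ratio flatters the intervention by crediting it with natural weight loss, and might attach a fold-error. With an assumed shared loss of 2, 5 or 10 kg and the numerator held fixed, (m + 2.1)/2.1 gives 1.95, 3.38 and 5.76. The documents do not support this as the size of the bias, for two reasons. First, those losses are plausible when counted from delivery, whereas Aim 5 speaks of change from baseline, which is about 10 weeks of gestation (D.12.1), and D.12.3 ties the weight measures to pre-pregnancy weight. The weight outcomes that Aim 5 names are GWG and postpartum retention, and for these the shared change may be a net gain. Second, once cost is differenced as well, at $300 against $150, the same three cases become 0.98, 1.69 and 2.88.

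Likewise, a null intervention would show a favourable ratio only if the comparison arm improved from baseline, and the documents give no comparison-arm mean.

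**Conclusion.** The Aim 5 definition is wrong as written. Neither the numerator nor the denominator is a between-arm difference, so the ratio does not measure what the Lifestyle Intervention buys over Health & Wellness. For GWG it has no improvement to divide by, provided that both arms gain weight.

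For the other outcomes, no single fold-error and no direction of bias should be claimed. Across the assumed range in the table, the incremental ratio lies between 0.26 and 3.86 times the written one, and at 3 kg net retention the written ratio turns negative. Those values rest on the Table 3 difference of 2.1 as the true effect and on assumed costs and comparison-arm changes.

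The problem is confined to Aim 5. Randomisation, sample size and the efficacy analyses of Aims 1-4 stand.

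**What to change.** Replace the definition in D.16 with: the ratio is (mean cost per woman in Lifestyle minus mean cost per woman in Health & Wellness) divided by the baseline-adjusted between-arm difference in change, taken from the mixed model already specified for Aims 1-3. For GWG, state the effect as kg of gain avoided relative to the comparison arm. If the cited procedures already work this way, say so in the same sentence.

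The cost is one paragraph of analysis text, plus costing of the comparison arm's mailings and calls. Section E (Sources of Materials) already plans to count sessions attended and booster calls taken part in; the authors should confirm that resource use is recorded in both arms. Sample size and outcome assessments do not change. A bootstrap interval for the ratio would be useful but is optional.

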Fasting Glucose (FG) will be measured enzymatically on the Roche P Modular system using Roche Diagnostics reagents (Indianapolis, IN).¹⁵⁵ Glucose at the concentrations of 90 and 312 mg/dL are determined in [name] laboratory with a day-to-day variability of 1.7 and 1.6%, respectively. Fasting Insulin (FI) will be measured by an electrochemiluminescence immunoassay on the Roche E Modular system. The lowest detection limit of this assay is 0.2 uU/mL and the day-to-day imprecision values at concentrations of 6.36, 20.9 and 747 uU/mL are 2.6, 2.8 and 2.5%, respectively. HOMA: Homeostasis model assessment will be calculated as [(FI x FG)/22.5] on a scale of 1-8. The Hemoglobin A1c (HbA1c) determination on the Roche P Modular system will be based on turbidimetric immunoinhibition using packed red cells. The day-to-day variability at values of 5.5 and 9.1 are 1.9 and 3.0%, respectively. Total Adiponectin (Multimeric) will be measured using an ELISA method from ALPCO Diagnostics Inc. (Salem, NH); day-to-day variabilities at concentrations of 9130 and 3930 are 9.8, 10.2%, respectively. Leptin will be measured by an ultra-sensitive ELISA assay, an enzymatically amplified “two-step” sandwich-type immunoassay (R&D Systems, Minneapolis, MN); day-to-day variability at concentrations of 65.7, 146 and 581 pg/mL are 5.4, 4.2 and 3.5%, respectively. Lipoprotein Profile: will be simultaneously performed on the Roche P Modular system. [name] laboratory is certified by the CDC/NHLBI Lipid Standardization Program.¹⁵⁶ Total Cholesterol will be measured enzymatically.¹⁵⁷ At cholesterol concentrations of 132.8 and 280.4 mg/dL, the day-to-day reproducibility are 1.7% (SD=2.4 mg/dL) and 1.6%, respectively. Triglycerides will be measured enzymatically with correction for endogenous glycerol.¹⁵⁸ Triglycerides at concentrations of 84.0 and 201.8 mg/dL have a day-to-day reproducibility of 1.8% (SD=1.6) and 1.7% (SD=3.5), respectively. The concentration of High Density Lipoprotein Cholesterol will be determined using a direct enzymatic colorimetric assay.¹⁵⁹ HDL-C at the concentrations of 27.0 and 54.9 mg/dL have a day-to-day reproducibility of 3.3 (SD=0.9) and 1.7% (SD=0.9), respectively. Low Density Lipoprotein Cholesterol will be determined by a homogenous direct method;¹⁶⁰ day-to-day variabilities at concentrations of 90, 106, and 129 mg/dL are 3.01, 2.34 and 2.18%, respectively. The concentration of High Sensitivity CReactive Protein (hsCRP) will be determined using an immunoturbidimetric assay on the Roche P Modular system using reagents and calibrators from DiaSorin (Stillwater, MN); day-to-day variabilities of the assay at concentrations of 0.91, 3.07 and 13.38 mg/L are 2.81, 1.61 and 1.1%, respectively.

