Pre-pregnancy BMI, weight at delivery, and gestational age at delivery will be abstracted from the medical record. Gestational age at delivery is recorded by the obstetrician at the time of delivery based on sonograms, date of last menstrual period (LMP), date the first fetal heart beat was heard with a stethoscope, and fundal height. Pregnancy weight is measured prospectively from all participants at each prenatal visit and postpartum weight will be measured by trained study staff to the nearest 0.1 kg on accurately calibrated standard clinical scales using a standardized protocol. Gestational weight gain will be calculated as the difference between maternal weight at delivery and pre-pregnancy weight. Rate of weight gain will be calculated as the difference between maternal weight at delivery and pre-pregnancy weight, divided by gestational age at delivery in weeks. Compliance with IOM weight gain guidelines will be calculated by comparing the observed weight gain with the 2009 IOM Guidelines⁷⁵ at that gestational age. Compliance will be specified as a continuous variable (percent of 2009 IOM Guidelines met) or as a categorical variable: inadequate, adequate, and excessive. Finally, we will measure the area under the gestational weight gain curve (AUC) since the time of randomization.¹⁵⁴ The AUC incorporates in a single statistic not only the final weight but also the trajectory to reach it and has been found to be a predictor of birthweight outcomes.¹⁵⁴ Postpartum weight loss will be calculated as: 1) absolute weight change at 6 and 12 mos postpartum according to pre-pregnancy BMI, 2) percentage who retain a specific amount of weight over pre-pregnancy weight, and 3) proportion whose BMI category changes from pre-pregnancy BMI category as have others.⁵⁹⁻⁶¹

D.12.4. Covariates

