We calculated the smallest mean difference in change from baseline in the Lifestyle Intervention vs. the Health & Wellness Control arm which we could detect at 80% power using standard deviations based on our prior studies and the literature^{47, 177-180} using 2-sided tests with a significance level of alpha=5% (NCSS PASS 2008 software). For multiple regression models, we assumed that covariates accounted for 20% of the variation. Tables 3 and 4 show we have excellent power to detect even ‘small to medium’ mean differences, as defined by Cohen,¹⁸¹ ranging from ~0.30 to 0.35 SDs for a range of representative outcome measures. For example, we have 80% power to detect as small as a 2.4% difference (Table 3) in percent change in HbA1c between treatment arms. A comparable trial among Hispanics observed a 7.1% difference in percent change in HbA1c between treatment arms¹⁸² demonstrating that detecting this difference is well within the capability of the lifestyle intervention. For the categorical outcome of Compliance with IOM GWG guidelines, given our observation that 51% of overweight/obese Hispanic women exceeded guidelines in the study population, we have 80% power to detect a 30% reduction in risk or larger for exceeding IOM guidelines.

Table 3. Power Calculations Corresponding to Aim #1-3.	Projected sample size for analysis	SD for Change from Baseline	Smallest detectable mean difference in change from baseline between arms
Aim #1: GWG & Postpartum Weight Loss			
GWG (kg)	300	7.00	2.3
Postpartum weight loss	264	6.00	2.1
Physical activity (MET-hrs/wk>mod intensity)	300	2.89	0.9
Physical activity (minutes>mod intensity)	300	38.05	12.3
Total Caloric Intake (kcal/day)	300	64.90	22.4
Aim #2: Biomarkers of Insulin Resistance			
Glucose (mg/dl)	300	13.27	4.3
Insulin (pmol/l)	300	14.20	4.6
HbA _{1c}	300	0.26	0.1
HbA _{1c} (percent change)	300	7.4%	2.4%
Adiponectin (μg/ml)	300	3.40	1.1
Leptin (ng/ml)	300	5.50	1.8
HOMA	300	1.00	0.3
Aim #3: Postpartum Biomarkers of CVD Risk			
Total cholesterol (mg/dL)	264	38.38	13.3
Triglycerides (mg/dL)	264	83.06	28.7
HDL-cholesterol (mg/dL)	264	7.59	2.6
LDL-cholesterol (mg/dL)	264	33.83	11.7
Systolic blood pressure (mm Hg)	264	12.23	4.2
Diastolic blood pressure (mm Hg)	264	7.64	2.6
CRP (mg/dl)	264	4.50	1.5

Table 4. Power Calculations Corresponding to Aim #4.	Projected sample size for analysis	SD	Smallest detectable mean difference between arms
Aim #4: Offspring Outcomes at Delivery			
Cord glucose (mg/dl)	288	14	4.6

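### D.16 puts the weight, insulin-resistance and cardiovascular outcomes under one primary analysis without naming a primary outcome, and leaves multiplicity to a judgement made after results are seen

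*Combined protocol and SAP*

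**What the plan says.** For Aims 1 to 3, D.16 (Statistical Analysis) states: "The primary analysis will evaluate differences in the change from baseline in weight gain measures, glycemia and other biomarkers of insulin resistance". The same sentence then adds the cardiovascular risk factors. The model is a mixed model with a baseline mean common to both arms, and "The intervention by period interaction is a measure of the intervention effect"; no period is singled out.

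D.17 (Power) gives a smallest detectable difference for each outcome separately, "using 2-sided tests with a significance level of alpha=5" percent, and describes the rows of Table 3 as representative. No adjusted level appears.

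The only provision on multiplicity is one sentence at the end of the missing-data paragraph of D.16: "Multiple comparisons will be addressed by carefully considering the biologic rationale of observed associations".

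D.12.3 lists several weight outcomes without ranking them: total gain, rate of gain, area under the gain curve and compliance with the Institute of Medicine (IOM) guidelines. On compliance: "Compliance will be specified as a continuous variable (percent of 2009 IOM Guidelines met) or as a categorical variable: inadequate, adequate, and excessive". On the period after delivery: "Postpartum weight loss will be calculated as: 1) absolute weight change at 6 and 12 mos postpartum", followed by two further measures.

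The supplied text, which starts at section D, contains no primary outcome, order of testing, split of alpha or success rule.

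**The concern.** A rule that weighs the biologic plausibility of associations already observed has no threshold and is applied once the results are known. It can exclude little here, because every listed outcome was chosen for its link to diet, activity and weight.

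D1 sets one overall goal, to test whether the intervention is efficacious, but nothing says which result would show that. A positive report could therefore rest on GWG, on one insulin-resistance marker or on one lipid, chosen after the fact. The error rate of such a selected claim is neither 5% nor stated. What is at stake is how far a headline conclusion of benefit could be trusted if only some outcomes are significant.

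**Working it through.** **1. Confirm that the plan uses an unadjusted 5% per outcome.** Detectable difference = (1.960 + 0.842) × SD × √(2/n per arm).
- GWG, SD 7.00, 150 per arm: 2.802 × 7.00 × √(2/150) = 2.26 kg. Table 3 gives 2.3; power at 2.3 kg is 81%.
- Postpartum weight, SD 6.00, 132 per arm (264 in all): 2.802 × 6.00 × √(2/132) = 2.07 kg. Table 3 gives 2.1; power at 2.1 kg is 81%.
- Glucose, SD 13.27, 150 per arm: 4.29 mg/dL. Table 3 gives 4.3.

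The tabled figures reproduce at 0.05 with no allowance for multiplicity.

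**2. Count the outcomes.** Table 3 has 19 rows. Dropping the three behaviour rows and the second HbA1c row leaves 15:
- two weight rows;
- six insulin-resistance rows (glucose, insulin, HbA1c, adiponectin, leptin, HOMA);
- seven cardiovascular rows (total cholesterol, triglycerides, HDL, LDL, systolic and diastolic pressure, CRP).

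**3. Chance of at least one significant result when nothing is affected.** With k independent tests it is 1 − 0.95^k two-sided. Counting only results that favour the intervention, it is 1 − 0.975^k. For correlated tests I assumed normal test statistics with a common correlation ρ, all oriented so that positive means benefit, and integrated numerically. The documents give no ρ, so the range is shown.

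| Set | Count | ρ = 0 | 0.3 | 0.5 | 0.7 | 0.9 |
|---|---|---|---|---|---|---|
| 15 rows | two-sided | 54% | 46% | 36% | 26% | 14% |
| 15 rows | favourable only | 32% | 23% | 18% | 13% | 7% |
| 7 cardiovascular rows (Aim 3) | two-sided | 30% | 27% | 23% | 18% | 11% |
| 7 cardiovascular rows (Aim 3) | favourable only | 16% | 14% | 11% | 9% | 6% |
| 6 insulin-resistance rows (Aim 2) | two-sided | 26% | 24% | 21% | 16% | 11% |
| 6 insulin-resistance rows (Aim 2) | favourable only | 14% | 12% | 10% | 8% | 5% |
| GWG and postpartum weight | two-sided | 9.8% | 9.5% | 9.1% | 8.4% | 7.0% |
| GWG and postpartum weight | favourable only | 4.9% | 4.8% | 4.5% | 4.2% | 3.5% |

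The benchmark for one test is 5% two-sided, or 2.5% in the favourable direction. HOMA is computed from insulin and glucose ("Homeostasis model assessment will be calculated as [(FI x FG)/22.5"]). Leaving it out gives 14 rows and 51/44/35/25/14% two-sided, so the result does not depend on it.

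**4. What is not counted.** D.12.1 lists six maternal blood collections, five of them after baseline, and D.12.3 gives alternative weight measures. The table uses one test per row.

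**The case against.** **By-aim reporting.** D.16 speaks of a primary analysis, partly in the sense of a method. It never declares co-primary outcomes, and it never says that one significant outcome would count as success. The aims are separate questions, and D.17 offers its rows as examples for power. This stands in part: if each aim is reported on its own, the 15-row figure is not the relevant error rate. The problem then remains within Aims 2 and 3, as the table shows. If success required every outcome to be significant, there would be no inflation. The plan fixes none of these rules.

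**Direction.** A reader might take 54% as the chance of a false claim of benefit. It is not: it counts results in either direction, and those pointing to harm could not support such a claim. The matching figures are the favourable-only ones. For the two weight outcomes these are 3.5 to 4.9%, above the 2.5% directional level but below 5%.

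**Definitions.** A reader might also infer that GWG itself is undefined. D.12.3 gives it one formula, delivery weight minus pre-pregnancy weight. D.17 powers IOM compliance as a categorical outcome. Table 3 uses 264 for postpartum weight, which matches "Therefore, we expect 264 women and children at 1 yr postpartum" and points to one year. What remains is that the list is unranked and 6 months is also named.

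**Interim knowledge.** D.19 says that analysis will be ongoing, and the safety-monitoring section puts preliminary analysis in the reports to the monitoring board. Neither says that results are shown by arm, so the documents do not support an inference that anyone choosing outcomes will have seen them.

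**Conclusion.** The concern holds in a limited form. No individual test is invalid, and the GWG test is sound at its own 5%. What is missing is a named primary outcome, a success rule and a multiplicity procedure that controls an error rate. The single sentence offered does not fill that gap.

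The consequence is conditional on a claim of benefit being selected across outcomes, or within Aim 2 or Aim 3, which the plan neither announces nor rules out. Its size depends on how many outcomes are in play and on their unknown correlation. Across all 15 rows, a false favourable finding has a probability of 7 to 32%, against 2.5% for one test. The range rests on all null hypotheses being true, one test per row and a common correlation between 0 and 0.9. It should be settled before results by arm are known, because a primary outcome chosen afterwards carries little weight.

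**What to change.** - Name one primary outcome with one definition and one time, tested at two-sided 5%. GWG as D.12.3 defines it is a natural example: it comes first in the aims, and its 2.3 kg detectable difference at N = 300 is unchanged.
- Those choosing must not have seen any comparison by arm. Record what had been seen when the choice was made.
- Label all other outcomes secondary or exploratory.
- Replace the biologic-rationale sentence with a prespecified procedure. One example: if the primary is significant, apply Holm to a short list with fixed times, and report the rest as exploratory or under false discovery rate control. The list and the method are the sponsor's choice.

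The change is to wording only; sample size and visits stay as they are. The cost is power for secondaries. Take three Holm secondaries, one of them postpartum weight at 1 year (132 per arm, SD 6.00 assumed to hold then). The strictest step uses 0.05/3 = 0.0167, with critical value 2.394.
- Standard error: 6.00 × √(2/132) = 0.7385 kg.
- Detectable difference: (2.394 + 0.842) × 0.7385 = 2.39 kg, against 2.07 kg at 5%.
- Power at 2.1 kg: 2.1/0.7385 = 2.843, and Φ(2.843 − 2.394) = 67%, against Φ(2.843 − 1.960) = 81%.

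The 67% is a floor once the primary has been passed, because later Holm steps are less strict. A shorter list would cost less.
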